#### 6.4.2 DOSE DELAY/MODIFICATIONS: UMBRALISIB (TGR-1202)

Supportive care should be considered for any subject who experiences Grade  $\geq 2$  cytopenias, or Grade  $\geq 1$  non-hematologic toxicities. If a subject experiences a treatment-related adverse event requiring dose modification during the course of therapy, then study drug administration should be held, as necessary, until the adverse event resolves or stabilizes to an acceptable degree. Contact TG Therapeutics prior to study drug re-initiation for dose delays exceeding 2 cycles with any questions. Time for recovery from toxicity is allowed for all study drugs (ublituximab and/or umbralisib: individually or together) to allow recovery of hematologic toxicities to  $\leq$  Grade 3 or non-hematologic toxicities to  $\leq$  Grade 2 or to baseline level. If a delay greater than 2-cycles is necessary for both study drugs, then notify TG Therapeutics prior to re-initiation. If the subject withdraws consent or has documented progression, an end of study visit should be completed.

If a subject discontinues only one study drug (either ublituximab or umbralisib), the subject may continue treatment with the other study drug per the protocol.

TABLE 4: UMBRALISIB DOSE DELAY AND/OR MODIFICATIONS GUIDANCE

NCI-CTCAE Grade	Dose Delay and/or Modification
Hematologic Adverse Event	
Neutropenia	
Grade $\leq 2$ neutropenia	Maintain current dose. Consider supportive care as warranted.
Grade 3 neutropenia	Maintain current dose, consider supportive care. If recurrence or persistent Grade 3, resume at next lower dose level at discretion of the investigator.
Grade 4 neutropenia or occurrence of neutropenic fever or infection	Delay umbralisib until Grade $\leq 3$ and/or neutropenic fever or infection is resolved; thereafter, resume at full dose. Consider supportive care.  If recurrence after rechallenge, resume at next lower dose level at discretion of the investigator.
Thrombocytopenia	
Grade $\leq 3$ thrombocytopenia	Maintain current dose level and provide supportive care as clinically warranted.
Grade 4 thrombocytopenia	Delay umbralisib until Grade $\leq 3$ ; thereafter, resume at full dose. Consider supportive care intervention as warranted.  If recurrence after rechallenge, resume at next lower dose level at discretion of the investigator.
Pulmonary & Related Infections*	
Grade 1 & 2	Withhold umbralisib as warranted, provide supportive care and hold until complete resolution. Resume umbralisib at one dose lower.  If recurrence after re-challenge, discontinue umbralisib.
Grade $\geq 3$	Discontinue umbralisib and intervene as warranted.
*For sinopulmonary infections clearly not related to immune-mediated pneumonitis, umbralisib may be continued at investigator's discretion. While pneumonitis has been minimal with umbralisib, it is a reported adverse event associated with other PI3K delta inhibitors. Use of anti-pneumocystis and anti-herpetic viral prophylaxis is required at start of therapy.	
Liver Toxicity (ALT/SGPT, AST/SGOT, Bilirubin, Alkaline Phosphatase)	

Grade 1	
 
Maintain current dose
 
Assess Concomitant Medications and Risk Factors*
 
Monitor Labs every 1-2 weeks
 

Grade 2	
 
Maintain current dose
 
Assess Concomitant Medications and Risk Factors*
 
Begin supportive care (40-60 mg prednisone orally per day or equivalent)**
 
Monitor labs at least weekly until Grade 1
 
Once resolved to Grade <math>\leq 1</math>, taper prednisone by 10 mg per week until off.                             
 
If liver toxicity recurs to Grade 2 once off steroids, re-initiate steroids with 10 mg per week taper until off.
 
Consider withholding umbralisib. If delay is greater than 2 cycles notify TG Therapeutics prior to re-initiating.
 
 
 

Grade $\geq 3$	
 
Hold Umbralisib. If delay is greater than 2 cycles notify TG Therapeutics prior to re-initiating.
 
Assess Concomitant Medications and Risk Factors*
 
Begin/continue supportive care (40-60 mg prednisone orally per day or equivalent)**
 
Monitor labs at least weekly until Grade 1
 
Once resolved to Grade <math>\leq 1</math>, taper prednisone by 10 mg per week until off
 
Resume -1 dose level when Grade <math>\leq 1</math>
 

* Assess for disorders of lipids and glucose, thyroid disorders, alcohol use, viral infections, etc.
 
**Supportive Care – Aggressive management of lipid, glucose, other metabolic disorders, viral infections, etc. Important: Before initiating steroids, check for viral hepatitis or CMV infection.
	
Diarrhea and/or Colitis	
Diarrhea Grade $\leq 2$	
Maintain current dose level if tolerable or hold and then resume at current dose level once has resolved.
 
NOTE: If persistent grade 2 diarrhea, despite supportive care, delay umbralisib until <math>\leq</math> grade 1. If recurrence after re-challenge, resume at full dose or next lower dose level at discretion of the investigator.

Diarrhea Grade $\geq 3$	
Withhold umbralisib until Grade <math>\leq 2</math>. Resume at full dose or next lower dose level as per discretion of investigator.
 
If recurrence after rechallenge, resume at next lower dose level at discretion of the investigator.

Colitis (all Grades)	
Hold umbralisib. Treat with supportive care and after resolution of colitis, resume umbralisib at next lower dose level.

All Other Non-Hematological Adverse Events	
Grade $\leq 2$	Maintain current dose level.
Grade $\geq 3$	
Withhold umbralisib until Grade <math>\leq 2</math>.
 
If recurrence after re-challenge, resume at full dose or next lower dose level at discretion of the investigator.

TABLE 5: STUDY DRUG DOSE LEVELS

Study Drug	Starting Dose	1 st Dose Reduction	2 nd Dose Reduction
Umbralisib	800 mg	600 mg	400 mg
A maximum of two dose level reductions are allowed for umbralisib.			

If a subject requires a dose reduction of umbralisib due to study drug related toxicity, the dose may not be re-escalated. If further evaluation of the toxicity reveals the event was not related to umbralisib, this must be recorded in the medical record and dose re-escalation to the next higher dose level may be considered at the discretion of the investigator.

---

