## STUDY SYNOPSIS

Protocol No.	UTX-TGR-204
Study Title	A Multi-Center, Open-Label, Compassionate Use Extension Study of Ublituximab (TG-1101) in Combination with Umbralisib (TGR-1202) for Patients Previously Enrolled in Protocol UTX-TGR-304
Sponsor	TG Therapeutics Inc. (New York, NY, USA)
Study Sites & Enrollment	This study will be opened only at sites that participate in the parent trial UTX-TGR-304 .
Study Rationale	
Ublituximab (also known as TG-1101) is a glycoengineered monoclonal antibody that binds to the trans-membrane antigen CD20 found on B-lymphocytes. The binding of ublituximab induces an immune response that causes lysis of B cells.
 
Umbralisib (also known as TGR-1202) is a highly specific and orally available phosphoinositide-3-kinase (PI3K) delta (<math>\delta</math>) inhibitor with nanomolar inhibitory potency, and high selectivity over the alpha, beta, and gamma Class I isoforms of PI3K. The delta isoform of PI3K is highly expressed in cells of hematopoietic origin, and strongly upregulated, and often mutated in various hematologic malignancies.
 
Ongoing studies are evaluating the combination of ublituximab + TGR-1202 in subjects who previously relapsed from or are refractory to anti-CD20 antibody therapy as well as PI3K delta inhibitor therapy (Lunning, et. al. ASCO 2015, Fowler, et. al. ASCO 2015). A Phase 3, randomized study (UTX-TGR-304) to assess efficacy and safety of ublituximab in combination with TGR-1202 compared to obinutuzumab in combination with chlorambucil in subjects with CLL is being conducted. UTX-TGR-304 will also compare ublituximab alone and TGR-1202 alone to the combination of ublituximab plus TGR-1202. This protocol is intended to provide the opportunity for subjects who progress on UTX-TGR-304 Treatment Arms B (obinutuzumab plus chlorambucil), C (ublituximab), or D (TGR-1202) to receive treatment with the combination. Additionally, at the time of UTX-TGR-304 study closure, this protocol is intended to allow subjects from Treatment Arm A (ublituximab plus TGR-1202) to continue combination therapy.

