
Dosing Regimen
	
Each Cycle = 28 days
 
Ublituximab + TGR-1202 Regimen
 
Subjects will receive ublituximab + TGR-1202 as described in protocol UTX-TGR-304. Subjects will receive TGR-1202 orally daily and ublituximab as an intravenous administration as per the schedule specified in the parent protocol and outlined in the table below. This schedule is specific to subjects that were in UTX-TGR-304 Arms B, C, and D. Subjects previously in Arm A of protocol UTX-TGR-304 will continue the schedule received while on study UTX-TGR-304 with TGR-1202 orally daily, and ublituximab every 3 months.
 
Cycle 1:
 
  
 Ublituximab	TGR-1202	
 
 Day 1	Day 2	Day 8 & 15	Daily	
   
 150 mg	750 mg	900 mg	800 mg	
  
 
Cycles 2 through 6:
 
  
 Ublituximab	TGR-1202	
   
 Day 1	Daily	
 
 900 mg	800 mg	
  
 
After Cycle 6:
 
  
 Ublituximab	TGR-1202	
   
 Day 1, Q3 months	Daily	
 
 900 mg	800 mg	
  
 
Ublituximab Premedication:
 
Ublituximab should be started approximately 30 minutes after the conclusion of the last pre-medication infusion and should include an antihistamine (diphenhydramine 50 mg or equivalent), and a corticosteroid (dexamethasone 10-20 mg or equivalent). If pre-medication is given orally, they should be given approximately 45-60
	Ublituximab			TGR-1202	Day 1	Day 2	Day 8 & 15	Daily	150 mg	750 mg	900 mg	800 mg	Ublituximab	TGR-1202	Day 1	Daily	900 mg	800 mg	Ublituximab	TGR-1202	Day 1, Q3 months	Daily	900 mg	800 mg
Ublituximab			TGR-1202																						
Day 1	Day 2	Day 8 & 15	Daily																						
150 mg	750 mg	900 mg	800 mg																						
Ublituximab	TGR-1202																								
Day 1	Daily																								
900 mg	800 mg																								
Ublituximab	TGR-1202																								
Day 1, Q3 months	Daily																								
900 mg	800 mg																								

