### 4.1 OVERVIEW OF STUDY DESIGN

---

This Companion Study is intended for subjects who previously enrolled to the parent trial [UTX-TGR-304](#). Subjects from Treatment Arms B, C, and D with disease progression confirmed by the independent review committee (IRC), may be enrolled into this Companion Study. At the end of the UTX-TGR-304 study, non-progressed subjects from Treatment Arm A may also be enrolled to this Companion Study. Subjects from Treatment Arms B, C, and D may start treatment with ublituximab + TGR-1202, while subjects entering the Companion Study from Treatment Arm A may continue their treatment as specified by this protocol. All subjects enrolled to the Companion Study should receive ublituximab in combination with TGR-1202 (at the same dose and schedule as the Treatment Arm A in UTX-TGR-304) until they show disease progression, are unable to continue treatment for any reason such as lack of tolerability, or until the treatment is commercially available.

During the study period, all subjects will be evaluated for response by CT and/or MRI. Evaluations are to be obtained at approximately cycles 3, 6 and 12. Following cycle 12, evaluations should occur at least every 12 cycles unless clinically indicated more frequently. Subjects should remain on study treatment until the occurrence of definitive disease progression, unacceptable toxicity, or withdrawal from the study due to investigator decision or other reasons. Subjects who discontinue from study treatment (either for toxicity or physician choice) and have not progressed should continue to be followed for progression per institutional standard of care and reported in eCRF. Date of progression, beginning of new treatment, and/or death should be entered in the eCRF.

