#### Treatment Schema for Subjects Crossing over from Arm A:

Subjects who crossover from Treatment Arm A will continue their treatment where they left off at the termination of [protocol UTX-TGR-304](#).

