#### Treatment Schema for Subjects Crossing over from Arms B and D:

##### Cycle 1:

Ublituximab			TGR-1202
Day 1	Day 2	Day 8 & 15	Daily
150 mg	750 mg	900 mg	800 mg

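### Every Arm D subject starts on umbralisib 800 mg, and the protocol does not say what happens if the dose was reduced for toxicity in Study 304

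*Combined protocol and SAP*

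**What the plan says.** **Prior exposure.** The synopsis rationale offers this study to subjects who progress on Arm B, "C (ublituximab), or D (TGR-1202) to receive treatment with the combination". Arm D subjects have therefore already taken umbralisib as a single agent. Inclusion criterion 1a requires at least two cycles of Study 304 treatment before entry.

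**Entry dose.** Section 6.1 has one schema, headed "Treatment Schema for Subjects Crossing over from Arms B and D", with umbralisib 800 mg daily in Cycle 1, in Cycles 2 to 6 and after Cycle 6. The synopsis gives the same doses and adds: "This schedule is specific to subjects that were in UTX-TGR-304 Arms B, C, and D". Section 4.1 has all enrolled subjects treated "at the same dose and schedule as the Treatment Arm A in UTX-TGR-304". None of the three mentions a subject whose dose had been lowered.

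**Arm A.** The only other group with prior umbralisib has a carry-over rule in Section 6.1: these subjects "will continue their treatment where they left off at the termination of" Study 304.

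**Dose reduction.** Table 5 in Section 6.4.2 sets a start of 800 mg, reductions to 600 mg and 400 mg, and no more than two reductions. The paragraph below it reads: "If a subject requires a dose reduction of umbralisib due to study drug related toxicity, the dose may not be re-escalated". The one exception is for an event later found unrelated to umbralisib; the investigator may then consider going up one level.

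**The concern.** Section 6.4.2 embodies a safety principle: once umbralisib has been lowered for drug-related toxicity, it stays lowered. Arm D is the progressing group to which that principle could already apply on the first day of this study, yet it shares a schema with Arm B, which had no umbralisib. Nothing in Section 6.1 or Table 5 provides for a lower start.

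Two entry doses can be argued for the same subject: 800 mg from Section 6.1, or the reduced dose if Section 6.4.2 is taken to reach back into Study 304. Without a written rule, the choice depends on how each site reads the text. A site that follows Section 6.1 gives a dose above the last one tolerated and adds a second drug. A site that enters the subject at 600 mg departs from the written schema. What is at stake is the safety of individual subjects; no claim is made about the analysis.

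**Working it through.** There is no figure in the plan to reproduce. The check compares the rules and then does simple dose arithmetic.

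**Step 1. Is there an exception anywhere?** Section 6.1, the synopsis and Section 4.1 give none. Exclusion criterion 1 sets a 7-day gap for Arm B and Arm C treatment only, so Arm D has no umbralisib washout. No exclusion criterion removes a subject with a toxicity-related reduction. The organ-function criteria look at current values, so a liver event that resolved on a lower dose would pass screening.

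**Step 2. Does Section 6.4.2 cover Study 304 reductions?** It neither includes nor excludes them. Its introductory text concerns adverse events arising on therapy, and Table 5 counts down from an 800 mg start; both fit an in-study reading. The sentence barring re-escalation carries no time limit of its own. The question is left open.

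**Step 3. Which events require a lower dose?** Table 4 has 15 rows: neutropenia 3 + thrombocytopenia 2 + pulmonary 2 + liver 3 + diarrhea/colitis 3 + other 2 = 15.

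| Instruction | Rows | Count |
|---|---|---|
| Lower dose after the first event | Liver Grade ≥3; colitis; pulmonary Grade 1–2 | 3 |
| Lower dose at the investigator's discretion | Neutropenia Grade 3 and Grade 4; thrombocytopenia Grade 4; diarrhea Grade ≤2 and Grade ≥3; other Grade ≥3 | 6 |
| Discontinue | Pulmonary Grade ≥3 | 1 |
| No reduction | The remaining rows | 5 |

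Check: 3 + 6 + 1 + 5 = 15. For liver the text is "Resume -1 dose level when Grade" ≤1 is reached; for pulmonary it is "Resume umbralisib at one dose lower". The pulmonary row carries a footnote: for sinopulmonary infections clearly not due to immune-mediated pneumonitis, umbralisib may be continued at the investigator's discretion. The mandatory reduction applies to the other Grade 1–2 pulmonary events.

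**Step 4. Size per affected subject.** Assume Study 304 used the Table 5 levels, and that the site follows Section 6.1.

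| Last Study 304 dose | Ratio | Increase | Extra per 28-day cycle |
|---|---|---|---|
| 600 mg | 800/600 = 1.33 | 33% | (800 − 600) × 28 = 5,600 mg |
| 400 mg | 800/400 = 2.00 | 100% | (800 − 400) × 28 = 11,200 mg |

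If the site instead applies Section 6.4.2 to the Study 304 reduction, the excess is zero.

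**Step 5. Reductions left.** If Study 304 reductions count, a subject entering at 600 mg has 2 − 1 = 1 left and one entering at 400 mg has 2 − 2 = 0. If they do not count, Table 5 allows two more from an 800 mg start.

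**The case against.** The strongest reply is that nothing conflicts. Read as an in-study rule, Section 6.4.2 begins at the Table 5 starting dose, and Section 6.1, the synopsis, Section 4.1 and Table 5 all agree on 800 mg. That reading is plausible. A reader might infer that Sections 6.1 and 6.4.2 contradict each other outright, but this holds only if the no-re-escalation rule reaches Study 304 reductions, which the text does not say. The silence remains, and it concerns a dose.

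Other points in reply:

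- **Arm A differs.** Its subjects have not progressed and simply continue, while Arm D starts a new combination, so different entry rules may be deliberate. This is fair; the contrast shows that the protocol considered carry-over for one exposed group, not that Arm D must follow the same rule.
- **A past reduction is not proof of intolerance.** In six rows of Table 4 the lower dose is discretionary, and entry to this study has no required timeframe, so the last dose may be old. A reader might infer that 800 mg is known to be intolerable for these subjects; the documents do not support that.
- **Safeguards exist.** Organ-function criteria apply at entry, chemistry and hematology are checked on Days 1, 8 and 15 of Cycle 1, and intolerable toxicity stops treatment. These would detect recurrence, but they do not set the entry dose.
- **The Study 304 protocol may contain the answer.** It is not among the documents, and the synopsis refers to it for dosing. If it holds such a rule, a cross-reference would suffice.
- **Larger increases.** Because the tablet is 200 mg, a reader might infer restarts from 200 mg. No dose ladder in the documents goes below 400 mg, so that figure has no support.

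**Conclusion.** The concern stands as an unaddressed gap. Section 6.1 starts every Arm D subject at 800 mg, and the protocol does not say whether a toxicity-related reduction in Study 304 binds the entry dose or uses up one of the two permitted reductions. Followed literally, Section 6.1 can place a subject 33% or 100% above the last tolerated dose with ublituximab added, contrary to the principle that Section 6.4.2 applies within the study.

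The percentages assume that Study 304 used the 800/600/400 mg levels. How many Arm D subjects were reduced and then enrolled cannot be learned from the documents and could be none, so no claim is made that anyone was or will be over-dosed. Severity is minor to should-fix: a cheap improvement for subject safety.

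**What to change.** In Section 6.1 and Table 5, state that:

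1. An Arm D subject whose umbralisib was reduced in Study 304 for umbralisib-related toxicity enters at the last tolerated Study 304 dose, unless the event was later judged unrelated to umbralisib (the existing Section 6.4.2 exception).
2. Reductions made in Study 304 count toward the maximum of two.

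At screening, record the last Study 304 umbralisib dose and the reason for any reduction. If the sponsor does intend a rechallenge at 800 mg, the text should say so and still settle the second item.

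**Cost.** Two or three sentences and one screening entry. Section 4.3 limits the study to Study 304 sites, so the entry can come from the existing record. No new procedure or tablet strength is needed (600 mg is three 200 mg tablets, 400 mg is two).

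**Downside.** Affected subjects, whose disease progressed on the umbralisib arm, start below 800 mg with fewer reductions left. For a subject entering at 400 mg, further toxicity calling for a reduction would end umbralisib, although Section 6.4.2 lets ublituximab continue.

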#### 6.4.3 ORDERING UBLITUXIMAB AND UMBRALISIB (TGR-1202)

---

Once a subject is identified, a shipment of pre-determined quantity of ublituximab and umbralisib will be shipped to the clinical study site.

Upon receipt of treatment supplies, the Pharmacist or the appropriate person of the site should update the accountability forms for both ublituximab and umbralisib. If any abnormality on the supplied boxes (ublituximab) or bottles (umbralisib) is observed, the Pharmacist or the appropriate person must document that on the acknowledgement of receipt and contact that Sponsor and/or Sponsor designee.

---

#### 6.4.4 DURATION OF THERAPY

---

In the absence of treatment delays due to adverse event(s), treatment should continue through Cycle 1 and beyond unless one of the following criteria applies:

- Disease progression or inter-current illness that prevents further treatment,
- Subject decides to withdraw from the study, or changes in the subject's condition render the subject unacceptable for further treatment in the judgment of the investigator.

During the study period, all subjects will be evaluated for response by CT and/or MRI. Evaluations are to be obtained at approximately cycles 3, 6 and 12. Following cycle 12, evaluations should occur at least every 12 cycles unless clinically indicated more frequently. Subjects will remain on study treatment until the occurrence of definitive disease progression, unacceptable toxicity, or withdrawal from the study due to investigator decision or other reasons. Subjects who discontinue from study treatment (either for toxicity or physician choice) and have not progressed should continue to be followed for progression per institutional standard of care.

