## 5.1 LABORATORY EVALUATIONS - OVERVIEW

All subjects should visit the study center on the days specified within this protocol. The complete schedule of assessments is shown in [Section 5](#). The baseline physical examination with vital signs, medical history, Rai staging, evaluation of concomitant medications, ECOG PS, bone marrow aspirate/biopsy (if applicable), complete blood count/full blood count (3-part differential accepted), serum chemistry, and CLL FISH panel, should be done within 28 days prior to initiation of treatment (14 days for CBC and Chemistry). For women of child bearing potential, a serum pregnancy test should be completed within 3 days (72 hours) prior to Day 1 of Cycle 1 and a urine pregnancy test within 3 days of assessment as per the [table in Section 5](#). Tumor assessment scans should be performed  $\leq 45$  days prior to initiation of treatment. In the event that the subject's condition is deteriorating, laboratory evaluations should be repeated within 48 hours prior to initiation of the next cycle of therapy.

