### 6.1 TREATMENT SUMMARY

---

Treatment will be administered on an outpatient basis in 4-week (28 day) cycles for subjects that roll over from 304 Arms B, C, and D.

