## 6.4 DOSING DELAYS/DOSE MODIFICATION

Subjects should be assessed clinically for toxicity at each visit using the NCI CTCAE v4.0 ([http://evs.nci.nih.gov/ftp1/CTCAE/CTCAE\\_4.03\\_2010-06-14\\_QuickReference\\_8.5x11.pdf](http://evs.nci.nih.gov/ftp1/CTCAE/CTCAE_4.03_2010-06-14_QuickReference_8.5x11.pdf)) grading scale. Dose delay and/or modification guidance is for adverse events considered at least possibly related to the study drug. If cytopenias are deemed related to the underlying disease rather than study drug, dose modifications are not required, or are per investigator discretion.

If greater than 2-cycle delay of treatment occurs for recovery of toxicities as outlined in Section 6.4 DOSING DELAYS/DOSE MODIFICATION, re-initiation of treatment is at the discretion of the investigator. Contact TG Therapeutics prior to re-initiating treatment with any questions. If a subject discontinues treatment due to toxicity, then the subject should continue to be followed for progression as described in [Table 2: FOLLOW UP ASSESSMENTS SCHEDULE](#). If a subject withdraws consent or has documented progression, an end of study visit should be completed.

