Worsening of disease during temporary interruption of study treatment (e.g., for intercurrent illness) is not necessarily indicative of resistance to study treatment. In these instances, CT/MRI or other relevant evaluations should be considered in order to document whether definitive disease progression has occurred. If subsequent evaluations suggest that the subject has experienced persistent definitive CLL progression, then the date of progression should be the timepoint at which progression was first objectively documented.

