## 9.8.2 SECONDARY EFFICACY VARIABLES

---

Progression free survival (PFS) is defined as the time from study entry to the first documentation of tumor progression or death due to any cause whichever comes first. For subjects previously on Arm A of Study UTX-TGR-304, PFS will be calculated from the date of randomization on Study UTX-TGR-304 to the first documentation of tumor progression or death due to any cause whichever comes first. This variable will be analyzed via Kaplan-Meier methodology. The median PFS will be estimated by treatment group, if appropriate (i.e., if sample sizes are sufficient) and overall.

MRD negativity rate is defined as the proportion of subjects who are MRD negative. This variable will be analyzed by the total number and percentage of subjects who are confirmed to achieve MRD negativity as per laboratory confirmation by treatment group and overall.

Duration of response is defined as the time from documentation of a response to treatment to the first documentation of tumor progression or death due to any cause whichever comes first. For subjects previously on Arm A of Study UTX-TGR-304, unless the subject's best overall response during study UTX-TGR-304 was stable disease, the duration of response will be determined from the first documented response on Study UTX-TGR-304. Duration of the response will be summarized using n (sample size), mean, standard deviation, median, minimum and maximum for the responders by treatment group and overall.

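### Response scans follow the cycle number and dose holds have no general limit, so if the count pauses, PFS and DOR dates depend on toxicity, with error of varying size and sign

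*Combined protocol and SAP*

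**What the plan says.** The scan schedule appears in the Synopsis (Study Design), Section 4.1, Section 5 Table 1, Section 6.4.4 and the opening of Section 8, each time by cycle number: "Evaluations are to be obtained at approximately cycles 3, 6 and 12. Following cycle 12, evaluations should occur at least every 12 cycles". Earlier scans are allowed when clinically indicated. Table 1 has visit windows for dosing, examinations and laboratory tests, but none for on-treatment scans.

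On holds, Section 6.4 begins a rule with "If greater than 2-cycle delay of treatment occurs for recovery of toxicities" and leaves restart to the investigator. Sections 6.3, 6.4.1 and 6.4.2 ask that the sponsor be notified when a delay exceeds 2 cycles. Certain toxicities require umbralisib to be discontinued, but no general maximum applies to a hold. The drugs may be held together or separately.

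Section 8.7 addresses "Worsening of disease during temporary interruption of study treatment" and asks that imaging be considered in that event. Follow-up imaging under institutional standard of care (Section 4.1, Table 2) applies to subjects who have stopped treatment, not to those on hold.

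Under Section 9.8.2, PFS and DOR both end at first documented progression or death, and DOR starts at a documented response. For PFS, "This variable will be analyzed via Kaplan-Meier methodology". No rule covers late or missed scans.

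**The concern.** When the assessment clock is tied to dosing, a subject who tolerates treatment and a subject held for toxicity are examined at different calendar times. Progression is dated when it is documented, so the recorded time mixes disease behaviour with tolerability. The Synopsis makes PFS and DOR primary objectives for subjects from Arm A and secondary for those from Arms B, C and D. Section 9.8.2 reports them by prior treatment arm, and hold rates may differ between arms. A difference in hold rates could then appear as a difference in PFS or DOR, and nothing in the analysis plan would reveal or correct it.

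**Working it through.** The plan gives no figure that depends on this point, so there is none to reproduce.

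**Inputs from the documents.** The Synopsis states "Each Cycle = 28 days". Cycles 3, 6 and 12 therefore end on days 84, 168 and 336 (3, 6 and 12 × 28), which are weeks 12, 24 and 48. Later scans are at most 12 × 28 = 336 days (48 weeks) apart. The 2-cycle notification point is 56 days (8 weeks).

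**Does the count pause during a hold?** No section says so.
- *For pausing:* Section 6.1 treats a cycle as a unit of treatment, "Treatment will be administered on an outpatient basis in 4-week (28 day) cycles", and Section 5.1 has "laboratory evaluations should be repeated within 48 hours prior to initiation of the next cycle of therapy". Ublituximab is due on Day 1 within ±3 days in Cycles 2 to 6 and within ±7 days afterwards. Table 3 delays and resumes it rather than skipping it, so an 8-week delay fits only if Day 1 moves.
- *Against:* a cycle has a fixed 28-day length, the hold rules use cycles as elapsed time, and if one drug continues the count need not stop.

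Pausing is the more natural reading when both drugs are held.

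**Assumptions (not in the documents).** The count pauses. PFS is exponential, S(w) = 0.5^(w/median), with median 52, 78 or 104 weeks. Progression is found only at scheduled scans. One hold of both drugs, of length h = 8 or 12 weeks, starts between the week-24 and week-48 scans.

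**Effect on one subject.** Scans at weeks 48, 96, … become 48+h, 96+h, …. With h = 8, progression at week 30 is recorded at week 56 instead of 48, which is 8 weeks later. Progression at week 50 is recorded at week 56 instead of 96, which is 40 weeks earlier.

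**Landmark PFS.** The recorded curve at any week equals S at the last scan done. If everyone still on treatment after week 24 is held:
- Week 52: S(24) is read instead of S(48).
- Week 60: S(48+h) is read instead of S(48).

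**Mean recorded PFS.** The mean is the sum over gaps of (gap length × S at the start of the gap). The change caused by the hold is h·S(24) − 48·(1 − S(h))·S(48)/(1 − S(48)). For median 52 and h = 8: 8 × 0.726 − 48 × 0.101 × 0.527/0.473 = 5.81 − 5.42 = +0.39 weeks.

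| Median (weeks) | 52 | 78 | 104 |
|---|---|---|---|
| S(24) | 0.726 | 0.808 | 0.852 |
| S(48) | 0.527 | 0.653 | 0.726 |
| S(56) | 0.474 | 0.608 | 0.689 |
| S(60) | 0.449 | 0.587 | 0.670 |
| Week-52 error | +0.199 | +0.155 | +0.126 |
| Week-60 error, h = 8 | −0.053 | −0.045 | −0.038 |
| Week-60 error, h = 12 | −0.078 | −0.066 | −0.056 |
| Mean change, h = 8 (weeks) | +0.39 | +0.27 | +0.21 |
| Mean change, h = 12 (weeks) | +0.80 | +0.57 | +0.44 |

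Errors use unrounded S. If 15% to 30% of those on treatment had such a hold (also an assumption), the group's week-52 estimate would be 0.15 × 0.126 = 0.019 to 0.30 × 0.199 = 0.060 too high.

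**Other hold timings.** A second calculation averaged over hold starts in the first 52 weeks, among subjects truly progression-free at hold start, with medians of 12 to 36 months. A 56-day hold changes the mean by −4.3 to −1.7 days. The sign differs from the table partly because this version excludes subjects whose progression before the hold had not yet been found.

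**When the shift is clearly upward.** In that second calculation, a 336-day hold with unchanged hazard adds 18 to 54 days. With the hazard tripled during the hold, a 168-day hold adds 10 to 33 days and a 336-day hold 59 to 144 days. For a 24-week hold between the week-24 and week-48 scans with tripled hazard, the first model gives about 3 to 6 weeks per held subject.

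**DOR.** By simulation, assuming response arises between days 28 and 150 and medians of 12 or 24 months, a hold in the first six cycles lowers mean DOR by about 26 to 30 days (56-day hold) or 70 to 74 days (112-day hold). The documented start moves later. Holds starting between days 168 and 336 change it by about −2 to −5 days.

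**The case against.** The strongest reply is that the premise is an inference. No section says that the count stops, a cycle is fixed at 28 days, and separate holds need not move anything. That stands, and the point is therefore conditional. But if the text can be read both ways, sites may differ, which is itself a reason to state the rule.

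The second reply is that the plan softens the effect. Scan timing is approximate, extra scans are allowed, Section 8.7 raises imaging when disease worsens during an interruption, and progression can also be shown by biopsy or by marrow-confirmed falls in blood counts. These limit the slippage, and the model's scan-only detection overstates it. None of them requires a scan during a hold.

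A reader might infer that late scanning always lengthens PFS and DOR, and the week-52 figures alone suggest it. The calculation does not support that. The whole later grid moves, so some progressions are documented earlier. The landmark error reverses once the delayed scan takes place, and an early hold can shorten DOR.

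Finally, Section 9.2 plans no hypothesis test, and the larger lag comes from the planned gaps. On an unshifted schedule with medians of 12 to 36 months, progression is still documented about 4.2 to 5.0 months late on average. Both facts limit the consequence. Neither justifies assessment times that depend on toxicity.

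**Conclusion.** The point holds as a defect in how scan timing is defined, not as an upward bias. Scans are numbered by cycle, holds have no general maximum, nothing keeps scans on schedule during a hold, and no analysis rule covers late scans. If the count pauses, the dates behind PFS and DOR depend on toxicity.

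For 8- to 12-week holds with unchanged hazard, mean documented PFS moves by less than about 1 week. Landmark PFS can be 13 to 20 points too high at week 52 and about 4 to 8 points too low by week 60 among held subjects. Those percentages take a whole group in which everyone still on treatment after week 24 is held. Only long holds, or a higher progression risk off drug, give a clear upward shift.

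All sizes rest on exponential PFS, scan-only detection and assumed hold lengths and timings; the documents give no hold rates. The week-24-to-48 calculation does not describe Arm A subjects, who enter mid-course. The results are descriptive, so this concerns how estimates by prior arm are read, not a test.

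**What to change.** In the Synopsis, Sections 4.1, 6.4.4 and 8, and Table 1, schedule scans by calendar time from Cycle 1 Day 1: about weeks 12, 24 and 48, then at least every 48 weeks. State a window, and add that the schedule applies regardless of dose delays or interruptions. Keep clinically indicated unscheduled scans. Table 1 places scans during the cycle, so the window should make clear that weeks 12, 24 and 48 are the ends of Cycles 3, 6 and 12.

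Subjects from Arm A resume where they left off in the parent study (Section 6.1), and their PFS runs from parent-study randomization (Section 9.8.2). Define an equivalent calendar anchor for them. A sentence in Section 9.8.2 on late or missed scans would complete the change.

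The dose-hold rules are untouched and the nominal frequency is unchanged. The cost is a short edit in five places plus the Arm A definition. Some scans will fall during a hold, and the lag from the planned 24- and 48-week gaps remains.
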